2 Only patients who have wild-type KRAS gene sequences at codons 12 or 13, or at codon 61 if it is tested, will be eligible. Testing may be performed at MD Anderson Cancer Center or an outside CLIA-certified laboratory. For testing at MD Anderson Cancer Center five unstained slides or a paraffin embedded tumor block are required. Tissue may be requested up to 6 weeks prior to first day of study treatment. In consenting patients, additional archival tissue may be collected at the same time for use in future research. Diagnostic imaging studies must be completed within 28 days prior to first day of study treatment. Hematologic, biochemistry, and serum pregnancy (if applicable) testing must be performed within 7 days prior to first dose of study drug. All other baseline evaluations must be completed within 10 days prior to first dose of study drug.

- 3 For Cycle 1, baseline evaluations will suffice if performed within 7 days prior to first dose of study drug.
- 4 Within 72 hours prior to start of the cycle (except for Cycle 1 as noted above).
- 5 Patient will be instructed to report any adverse events to the research nurse at least once weekly (+/- 1 day).
- 6 Imaging should be obtained every 4 cycles (+/- 1 week allowance is made for scheduling). . After a tumor evaluation is performed which demonstrates a tumor response (partial or complete), confirmation of the response may be obtained by a second evaluation to be performed 3 cycles later.
- 7 For patients taken off study treatment for reasons other than progression, perform every 12 weeks (+/- 2 week allowance is made for scheduling) after the End of Treatment Evaluation visit until documentation of progression if no other anti-cancer treatment is given.
- 8 CT scans or other imaging modality. MRI may be used in cases where it is felt to be unsafe to perform CT secondary to patient's history of dye allergy, or if the tumor is not adequately seen on CT for the purposes of this study.
- 9 Treatment-related adverse events occurring during study treatment or within 30 days after the last administration of study drug(s) will be followed until resolution or stabilization. If the patient is unable or unwilling to return to M. D. Anderson for this assessment, the patient will be contacted by phone for this assessment.
- 10 Every 3 months (+/- 2 weeks) from Post-Treatment Evaluation.

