- 11 Hematology: hemoglobin, platelets, and absolute neutrophil count. Chemistry: creatinine, total bilirubin, AST, ALT, Magnesium, Potassium, Calcium. In patients with known Gilbert's syndrome direct bilirubin will also be performed
- 12 At time of or up to 10 days after decision to discontinue study treatment.
13. Up to 35 days from last dose of study medication.

Statistical Considerations:

Study design and Sample Size:

Amended Study Design, Sample Size, Efficacy and Toxicity Monitoring as of October 1, 2012:

The primary endpoint of this phase II, single arm study is response rate (RR) for patients treated with single-agent Panitumumab. Patients will be evaluated for up to 8 cycles from their first dose, and a patient will be considered as a non-responder if no PR or CR has been documented after 8 cycles of treatment. Patients who withdraw early will be included in the ITT analysis. Based on our current data with a null hypothesis of $\leq 1\%$ RR to an inactive drug for refractory patients, a sample size of 17 patients with Panitumumab would be required to demonstrate a response rate of 17% using a binomial one-sample test with a two-sided alpha of 0.05 and power of 90%.

The primary adverse event to be monitored will be the toxicity rate. Toxicities to be included in toxicity monitoring include definite or probably treatment-related grade 3 or 4 non-hematological toxicities, excluding grade 3 rash and grade 3 hypomagnesemia, which are both expected and manageable toxicities. Only toxicities during the first 4 cycles of therapy will be used in toxicity monitoring. Accrual is estimated at 1 to 2 patients per month.

Sample Size and Endpoint Monitoring

Response and toxicity will be monitored simultaneously using the Bayesian approach of Thall, Simon, Estey (1995, 1996) and the extension by Thall and Sung (1998). Data from a previous study of single agent Panitumumab in Kras wildtype colorectal cancer demonstrated a response rate for Panitumumab is approximately 17%. The toxicity rate of Panitumumab will estimate it will be approximately 25%. For the prior distribution of standard Panitumumab, we assumed a simple Dirichlet distribution and independence between OR and toxicity in 124 patients. The parameters for this prior distribution are as follows:

Dirichlet parameters for the joint prior distribution of objective response and toxicity rate assuming information on 124 patients and independence among response and toxicity for Panitumumab.

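### The only primary endpoint does not require responses to be confirmed, and against a 1% null in 17 patients one unconfirmed reading can change the formal test result

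*Combined protocol and SAP*

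**What the plan says.** Under Statistical Considerations (amended design of October 1, 2012): "The primary endpoint of this phase II, single arm study is response rate (RR) for patients treated with single-agent Panitumumab". The responder rule follows: "a patient will be considered as a non-responder if no PR or CR has been documented after 8 cycles of treatment". It does not ask for confirmation. Early withdrawals stay in the denominator: "Patients who withdraw early will be included in the ITT analysis".

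The only sentence on confirmation is in footnote 6 of the Study Calendar, which puts restaging at every 4 cycles and adds, for a PR or CR, that "confirmation of the response may be obtained by a second evaluation to be performed 3 cycles later". Nothing else in the document makes confirmation compulsory. RECIST 1.1 is cited only for measurable disease at entry (Inclusion 4), and no independent image review is described. The Proposed Treatment/Study Plan describes a single-centre, open-label, single-arm study.

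The formal test is a one-sample binomial test of a null of at most 1% against 17%, with 17 patients, two-sided alpha 0.05 and 90% power. Sample Size and Endpoint Monitoring adds a futility stop at 0 responses in the first 8 patients. It also says the regimen would merit further study if the response rate rose to 25% with acceptable toxicity.

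**The concern.** The treating centre reads the scans knowing the treatment, there is no control arm, and a single reading of PR or CR is enough to count. With a null as low as 1%, the test leaves little room for reading error. If some first readings are not borne out on a second scan, the reported response rate is too high, and an inactive drug is more likely to pass the test than the nominal level implies. The count is also small enough that one patient's classification can settle the formal result.

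**Working it through.** **Inputs.** Null 1%, alternative 17%, N = 17, two-sided alpha 0.05 (0.025 in the upper tail) and the 0/8 futility rule, all from Statistical Considerations. The false-reading rates and the fractions failing to confirm are assumptions; the documents give neither.

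**The plan's own figure.** The normal approximation gives n = [(1.960·√(0.01·0.99) + 1.282·√(0.17·0.83)) / 0.16]² = 17.87, so 18, one more than the stated 17. Approximate power at 17 is 89.2%. The stated design is therefore close to reproduced. Exact power is lower, as shown below; that is a separate matter.

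**Critical count.** No critical number is printed, so it is derived from the stated test. At a 1% rate:
- P(0 of 17) = 0.99¹⁷ = 0.8429
- P(exactly 1) = 17·0.01·0.99¹⁶ = 0.1447
- P(at least 1) = 0.157
- P(at least 2) = 0.0123

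Only the last is below 0.025, so two responses reject and one does not. Exact 95% lower limits agree: 1.46% for 2/17 and 0.15% for 1/17. This step needs no assumption about reading error.

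**Sensitivity to false readings.** Let p be the apparent response rate on an inactive drug.
- Without the stop: A = P(at least 2 of 17 | p).
- With the stop: B = A − (1−p)⁸ · P(at least 2 of 9 | p). A trial stopped at 0/8 counts as not rejecting, and the first 8 patients are assumed to be assessed before accrual goes on.

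| p | A | (1−p)⁸ | P(≥2 of 9) | B |
|---|---|---|---|---|
| 1% (stated null) | 1.2% | 0.9227 | 0.0034 | 0.9% |
| 2% | 4.5% | 0.8508 | 0.0131 | 3.3% |
| 3% | 9.1% | 0.7837 | 0.0282 | 6.9% |
| 4% | 14.7% | 0.7214 | 0.0478 | 11.2% |
| 5% | 20.8% | 0.6634 | 0.0712 | 16.1% |

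The 0.025 level is exceeded at 2% with or without the stop. An apparent 2% needs a false-reading chance of only about 1% per patient: 0.01 + 0.99·0.01 = 0.0199.

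**The other success statement.** 2/17 = 11.8% and 4/17 = 23.5%. An observed rate of at least 25% needs 5/17 = 29.4%. At p = 5%, P(at least 5 of 17) is 0.12%.

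**Cost of requiring confirmation.** Suppose 17% is an unconfirmed rate and a fraction c of responses confirm, so p = 0.17c. The stop is applied to unconfirmed responses, so P(0/8) stays at 0.83⁸ = 0.2252, and power with the stop is P(≥2 of 17 | p) − 0.2252·P(≥2 of 9 | p).

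| c | p | Power, no stop | P(≥2 of 9) | Power with stop |
|---|---|---|---|---|
| 1 | 17% | 81.1% | 0.4685 | 70.6% |
| 0.9 | 15.3% | 75.8% | 0.4109 | 66.6% |
| 0.8 | 13.6% | 69.4% | 0.3516 | 61.5% |

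**The case against.** Unconfirmed response is an open and defensible choice for a signal-finding phase II trial. Several stronger readings that a reader might infer do not hold.

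- **Two definitions are mixed because confirmation is optional.** The documents do not support this. The responder rule is the same for everyone, and nothing says that a confirmatory scan, whether done, skipped or failed, alters a patient's status. The rule is lenient but uniform.
- **The plan contradicts itself on timing.** A response first seen at cycle 8 would have its optional scan near cycle 11, after the 8-cycle window. That matters only once confirmation is required. An optional scan off the 4-cycle grid is just an extra scan.
- **Two responses make the trial a success.** They reject the 1% null, but they fall short of the 25% criterion. The plan does not say which criterion governs.

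Three further points stand. The 2–5% range has no source in the documents. The 1% null is said to rest on the sponsor's current data, and if those data used unconfirmed readings, some reading error is already in the 1%. And requiring confirmation has a price: if it also governed the interim count, each responder's classification would wait another 4 two-week cycles in a trial monitored patient by patient, and 10–20% non-confirmation would raise the chance of 0/8 from 22.5% to 26.5–31.1%. Patients off treatment are not on the 4-cycle schedule at all.

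None of this alters the fact that the count behind the formal test rests on readings that need not be repeated.

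**Conclusion.** The point holds as a weakness in a stated rule, and it should be changed. Without any assumption about error rates, one unconfirmed reading separates 1/17 (P = 0.157) from 2/17 (P = 0.012), and 0/8 from 1/8.

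The inflation figures are conditional. They assume that false readings add to a true 1% rate, and they show how little error is needed rather than how much there is. A reader might infer that the type I error is in fact inflated; the documents give no reading-error rate to establish that. A reader might also judge the figures against 0.05 and conclude that the level holds until about 3%. The stated test is two-sided, so the benchmark is 0.025.

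The formal test and the 25% criterion must be reconciled before any single count can be called the trial's success rule.

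**What to change.** For the final primary analysis:

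1. Define response as PR or CR first documented by the end of cycle 8 and confirmed at the next scheduled restaging. That is 4 cycles later on treatment, or the footnote 7 imaging for patients off treatment without progression.
2. State that this confirmation may fall after cycle 8, and that a response without a confirmatory scan counts as non-response.
3. Keep the interim futility count on first-documented responses, so that monitoring is not delayed.
4. Report the unconfirmed rate as a sensitivity analysis.
5. State whether the 1% null and the 17% alternative are confirmed rates, and reconcile the test with the 25% criterion.

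The cost is a wording change and a later final read for late responders. Patients still on treatment use scans already planned. Patients off treatment are imaged every 12 weeks, and only if no other anti-cancer treatment is given, so some of their responses will go unconfirmed. If 17% is already a confirmed rate, no power is lost; otherwise the loss is as tabulated, under the assumed 10–20% non-confirmation. The document records accrual as closed, so the change would apply to analysis and reporting. If responses have already been seen, show both rates and label the confirmed definition as added later.

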	No Response	Response
No Toxicity	77	16
Toxicity	26	5

A flat Dirichlet prior distribution for experimental Panitumumab was chosen reflective of information from the equivalent of 4 patients with the same marginal distributions as for Panitumumab (e.g., RR rate of 17% and toxicity rate of 25%).

This regimen of Panitumumab will be considered worthy of further investigation if it elicits an increase in RR to 25% with acceptable toxicity. A 25% toxicity rate is considered unacceptable. Thus, interim monitoring rules, assuming the prior distributions above, were constructed that meet the following two conditions,

- 1) $\Pr(\emptyset_S, \text{Toxicity} < \emptyset_E, \text{Toxicity} \mid \text{data}) > 0.95$ and,
- 2) $\Pr(\emptyset_S, \text{Response} < \emptyset_E, \text{Response} \mid \text{data}) < 0.05$

Where $\emptyset_{E, \text{Toxicity}}$ and $\emptyset_{E, \text{Response}}$ are the true toxicity and response rates for Panitumumab, respectively. The first rule provides for stopping the study if excessive toxicity is highly probable (i.e., probability $> 95\%$) for Panitumumab. The second condition will stop the study early if the data suggest that it is unlikely (i.e., probability $< 5\%$) that response rate

of the drug is 17%. Assuming the minimum number of patients is 1, the maximum number of patients is 17 and the cohort size is 1.

The monitoring rule for the toxicity rate, based on these assumptions and monitoring conditions above is found in the following table. For example, accrual will cease if 4 or more patients experience toxicities among the first 5 patients treated or if 6 or more patients experience toxicities among the first 10 patients.

Stop accrual if the number of toxicities is equal to or greater than indicated (i.e., # toxicities) among the number of patients evaluated (i.e., # patients)						
# Toxicities	3-4	4-6	5-9	6-11	17-14	8-16
# Patients	3-4	5-6	7-9	10-11	12-14	15-16

Monitoring the response rate, based on the above assumptions and monitoring will begin after 1 patient is treated (on an intent-to-treat basis). Following this rule, the trial will be terminated if $[\# \text{ Response}] / [\# \text{ patients evaluated}] \leq 0/8$. For example, accrual will cease if 0 or fewer patients experience a response in the first 8 patients treated.

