Multc Lean Desktop (version 2.0.0) was used to generate the toxicity and futility stopping boundaries and the OC table. In order to utilize the software for the design, a beta (21, 103) prior was assumed for the historical control response rate and a beta (31, 93) prior was assumed for the historical control toxicity rate.

The probability of stopping the study early if the true response rate of the Panitumumab was not better than 17% was 35%. Probabilities of stopping early for high true toxicity rates (i.e., 37%) were 57% when the true RR rate was 17% and 48% when true RR was 25%.

Operating characteristics for simultaneous monitoring response and toxicity rates for patients treated with Panitumumab.				
True RR	True Toxicity Rate	True Probability Vector (RR/TX, RR/NTX, NRR/TX, NRR/NTX)	Probability of Stopping	Average number of patients treated
8%	12%	(0.010,0.070,0.110,0.810)	0.5174	12
8%	25%	(0.020,0.060,0.230,0.690)	0.5637	12
8%	37%	(0.030,0.050,0.340,0.580)	0.6885	10
17%	12%	(0.020,0.150,0.099,0.730)	0.2319	15
17%	25%	(0.042,0.127,0.207,0.622)	0.3055	14
17%	37%	(0.062,0.107,0.307,0.523)	0.5042	12
25%	12%	(0.030,0.220,0.090,0.660)	0.1078	16
25%	25%	(0.062,0.187,0.187,0.562)	0.1934	15
25%	37%	(0.092,0.157,0.277,0.472)	0.4241	13

Where Will Participants Be Enrolled:

Only at MDACC

Is this an NCI-Cancer Therapy Evaluation Protocol (CTEP)? No

Is this an NCI-Division of Cancer Prevention Protocol (DCP)? No

Estimated Accrual:

Total Accrual at MDACC: 27

Estimated monthly accrual at MDACC: 1-2

Accrual Comments:

The total accrual for this study is 27. There are 10 patients already enrolled and 3 have been treated with combination therapy, and 17 patients are to be enrolled for the single agent treatment.

Do you expect your target population to include non-english speaking participants? No

Location of Treatment:

This protocol is performed on an Outpatient basis.

Length of Stay: What is the length & frequency of hospitalization?

NA

Return Visits: How often must participants come to MDACC?

Every 2 weeks

Home Care: Specify what, if any, treatment may be given at home.

NA

Name of Person at MDACC Responsible for Data Management: [[name]](#)

Prior protocol at M. D. Anderson:

Has the Principal Investigator ever had a clinical or behavioral protocol at MDACC that accrued patients?
Yes

Data Monitoring Committee:

Is treatment assignment randomized? No

Is this a blinded or double-blinded study? No

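### The stated 90% power for 17 patients (17% versus 1% or less) is wrong: an exact test that holds alpha has 81.1%, and about 71% once the 0/8 futility rule is applied

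*Combined protocol and SAP*

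**What the plan says.** Response rate is the primary endpoint. In Statistical Considerations, Study design and Sample Size (amended October 1, 2012), the null is a response rate of at most 1%. The text reads "RR to an inactive drug for refractory patients, a sample size of 17 patients with Panitumumab would be required", and the target is a "response rate of 17% using a binomial one-sample test with a two-sided alpha of 0.05 and power of 90" per cent. The section does not say whether the binomial test is exact or approximate, and it gives no number of responses that would reject the null. On classification it states that "a patient will be considered as a non-responder if no PR or CR has been documented after 8 cycles of treatment", and on dropout that "Patients who withdraw early will be included in the ITT analysis".

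Sample Size and Endpoint Monitoring adds a futility rule, repeated under Data Monitoring Committee: "accrual will cease if 0 or fewer patients experience a response in the first 8 patients treated". The table headed "Operating characteristics for simultaneous monitoring response and toxicity rates for patients treated with Panitumumab" gives probabilities of early stopping. At a true response rate of 17% they are 0.2319, 0.3055 and 0.5042 for toxicity rates of 12%, 25% and 37%. The table gives no power for the test against 1%, and the power sentence does not mention stopping.

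**The concern.** With a null rate of 1% and 17 patients, the expected number of responses under the null is 17 × 0.01 = 0.17. The distribution is then so coarse that only two cut-offs are worth considering, 1 or 2 responses, and a large-sample formula cannot be relied on. A power of 90% also implies a 10% chance of missing a true 17% rate, yet the plan's own table shows the trial stopping early at least 23% of the time at that rate.

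Two things are at stake. First, this sentence is the only power justification for the sample size. Second, because the form of the test and its cut-off are not stated, one response in 17 would be positive under the approximation and negative under an exact test.

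**Working it through.** **Inputs.** Null rate p0 = 0.01 (the upper limit of the stated null), alternative p1 = 0.17, n = 17, two-sided alpha 0.05, all from Study design and Sample Size. The futility stop at 0/8 comes from Sample Size and Endpoint Monitoring. There is no dropout inflation.

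**1. Where the 90% comes from.** The uncorrected normal approximation uses the null variance under the null and the alternative variance under the alternative: √(0.01 × 0.99) = 0.0995 and √(0.17 × 0.83) = 0.3756.

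- Two-sided 0.05: power = Φ[(0.16 × √17 − 1.960 × 0.0995) / 0.3756] = Φ(1.237) = 89.2%. The sample size for 90% is [(1.960 × 0.0995 + 1.2816 × 0.3756) / 0.16]² = 17.87.
- One-sided 0.05: power 90.7%, n = 16.25, which rounds up to 17. The plan states two-sided.

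That z test rejects at one response: (1/17 − 0.01) / √(0.01 × 0.99 / 17) = 2.02.

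**2. Exact binomial, n = 17.**

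| Reject if at least | Size at 1% | Power at 17% |
|---|---|---|
| 1 of 17 | 1 − 0.99¹⁷ = 15.7% | 95.8% |
| 2 of 17 | 1.23% | 81.1% |
| 3 of 17 | 0.06% | 57.1% |

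The cut-off that holds alpha is 2, whether the upper tail is held to 0.025 or 0.05. Power at 2 is 1 − 0.83¹⁷ − 17 × 0.17 × 0.83¹⁶ = 1 − 0.0421 − 0.1466 = 0.8113. Even a randomised test that uses up the whole alpha reaches only 82.4% (upper tail 0.025) or 84.9% (one-sided 0.05). The smallest sample with exact power of at least 90%, before futility, is 22 (at least 2 responses, size 2.0%, power 90.9%).

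**3. Adding the 0/8 rule, binding and without overrun.**

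- P(0/8 at 17%) = 0.83⁸ = 0.2252, so power cannot exceed 1 − 0.2252 = 77.5% whatever the cut-off.
- Power = P(at least 2 of 17) − 0.83⁸ × P(at least 2 of the last 9) = 0.8113 − 0.2252 × 0.4685 = 0.7058.
- Size by the same formula at 1% = 0.9%.
- At a true rate of 25%, which the plan calls worthy of further investigation: 95.0% without monitoring, 88.0% with the rule.

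**4. Check against the plan's own table.** I enumerated patient by patient with the 0/8 rule and the toxicity boundaries read as 3 (at 3–4 patients), 4 (5–6), 5 (7–9), 6 (10–11), 7 (12–14) and 8 (15–16), taking response and toxicity as independent. The fifth boundary is printed as 17-14, and I read it as 7. All nine stopping probabilities are reproduced. At 17% response and 12% toxicity, 0.2319 splits into 0.2236 for futility and 0.0083 for toxicity. The table therefore treats 0/8 as binding with no overrun, the same basis as step 3.

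**5. Counting overrun.** Settling non-response takes up to 8 cycles of two weeks, or 16 weeks. At 1 to 2 patients per month, about 4 to 7 more patients would be enrolled while the eighth outcome is pending. If they count, and success still needs at least 2 responses:

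- 4 patients: 0.7058 + 0.2252 × 0.1366 = 73.7% (size 0.97%).
- 7 patients: 0.7058 + 0.2252 × 0.3396 = 78.2% (size 1.10%).

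**The case against.** The plan says binomial, not exact. The usual normal-approximation formula lands on the stated figure within rounding (89.2% two-sided, 90.7% one-sided), so it can be argued that the 90% is reproducible and merely rests on a poor approximation. That explains its origin but does not rescue it. The test that goes with the formula rejects at one response, and its true size is 15.7%, or 1 − 0.99⁸ = 7.7% if 0/8 is binding. Both exceed the stated 5%. The unmonitored power of 95.8% under that test is bought with that error rate, and with 0/8 binding it falls to 77.5%.

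A second objection is that the 71% is a different quantity from fixed-sample power. It needs a binding rule, no overrun, and a stopped trial counted as not positive, while the stopping table already discloses the cost. The conditions are real and belong beside the number. The 81.1% is the correction that needs none of them. The overrun range is also assumption-dependent, since progression found at the first restaging after 4 cycles would shorten the wait. But every figure in the range is well below 90%, and the table is never carried into the power claim.

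Finally, the study is recorded as closed to entry on 04/26/2016, so the sample size cannot be rebuilt, and at a true rate of 25% power is close to the advertised level. Both points stand. They limit the remedy to wording, but the power claim is made at 17%.

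**Conclusion.** The concern holds. Alpha of 0.05 and power of 90% at a 17% response rate cannot both be true with 17 patients. The chance of failing to show a true 17% rate is 19% without monitoring and about 29% with the printed futility rule, against the 10% implied.

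These figures take the null at its 1% limit and use the exact test with a cut-off of 2. The 29% also takes 0/8 as binding with no overrun; counting 4 to 7 overrun patients brings it to between 26% and 22%. Toxicity stopping is left out of these figures. If it is included, the chance of completing accrual with at least 2 responses at a 17% rate is 70.0% at 12% toxicity and 63.3% at 25%, but a toxicity stop is not an efficacy failure and should be reported separately.

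**What to change.** Replace the power clause in Study design and Sample Size with wording such as:

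> The primary analysis is an exact one-sample binomial test. A response rate of 1% or less is rejected if at least 2 of 17 patients respond (one-sided size 0.012). At a true response rate of 17%, power is 81% without monitoring and about 71% with the 0/8 futility rule applied as in the operating characteristics table.

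State also whether patients already enrolled when 0/8 is reached are counted in the intention-to-treat analysis. If they are, give the matching power (73.7% to 78.2% for 4 to 7 such patients). The chance of completing accrual with at least 2 responses, allowing for toxicity stops, can be added as a separate line.

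The cost is wording only: no extra patients and no change to any boundary. The stated power becomes less favourable, and the text should say openly that 17 patients is accepted at that level, since exact 90% power would have needed 22 before futility.
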